3.2.1. Dose Selection

Data from two dose ranging studies, AC4113073 and AC4113589, demonstrated significant improvements in lung function for UMEC as measured by FEV₁ over 24 to 28 hours. However, there was no clear dose differentiation over the range of once-daily doses tested (62.5 mcg and 1000 mcg). A third dose ranging study (AC4115321), evaluating lower doses of UMEC monotherapy once and twice daily in COPD, demonstrated a FEV₁ dose response across the range of once-daily doses of UMEC tested (15.6 to 125 mcg) supporting the dose selection for Phase IIIa. This third study further substantiated the findings from the previous dose ranging study (AC4113073) by showing twice-daily doses did not provide added benefit over once-daily dose, supporting a once-daily dosing interval. Based on a favourable therapeutic index, two doses of UMEC were selected to be taken to Phase III, 62.5 mcg and 125 mcg.

Integrated analysis of Phase IIIa study lung function parameters and rescue medication data indicates that differences in response to the 125 mcg dose and the 62.5 mcg dose, were modest, were not always consistently observed and were not considered clinically meaningful. TDI score and SGRQ changes also did not show an advantage for the 125 mcg dose versus 62.5 mcg and the sub-group analysis did not identify a group who benefited from UMEC 125 mcg versus the 62.5 mcg. Therefore, the 62.5 mcg is the most appropriate dose for the treatment of COPD patients.

4. SUBJECT SELECTION AND WITHDRAWAL CRITERIA

4.1. Number of Subjects

Based on an early withdrawal rate of 18% of randomized subjects, approximately 288 study subjects will be randomized in 2:1 to the double blind medication, that means 192 subjects in active arm and 96 subjects in placebo arm, to ensure approximately 236 subjects complete the 24 week treatment period.

4.2. Inclusion Criteria

Specific information regarding warnings, precautions, contraindications, adverse events, and other pertinent information on the GSK investigational product or other study treatment that may impact subject eligibility is provided in the IB/IB supplement(s).

Deviations from inclusion criteria are not allowed because they can potentially jeopardize the scientific integrity of the study, regulatory acceptability or subject safety. Therefore, adherence to the criteria as specified in the protocol is essential.

Subjects eligible for enrolment in the study must meet all of the following criteria:

1. **Type of subject:** outpatient, Asian ancestry.
2. **Informed Consent:** A signed and dated written informed consent prior to study participation.
3. **Age:** 40 years of age or older at Screening (Visit 1).
4. **Gender:** Male or female subjects are eligible to participate in the study.

A female is eligible to enter and participate in the study if she is of:

Non-child bearing potential (i.e. physiologically incapable of becoming pregnant, including any female who is post-menopausal or surgically sterile). Surgically sterile females are defined as those with a documented hysterectomy and/or bilateral oophorectomy or tubal ligation. Post-menopausal females are defined as being amenorrhoeic for greater than 1 year with an appropriate clinical profile, e.g. age appropriate, >45 years, in the absence of hormone replacement therapy. However, in questionable cases, post-menopause status may be confirmed by analysis of a blood sample with Follicle Stimulating Hormone (FSH) >40MIU/ml and estradiol <40pg/ml (<140 pmol/L) as confirmatory.

OR

Child bearing potential, provided the subject has a negative pregnancy test at screening, and agrees to one of the following acceptable contraceptive methods used consistently and correctly (i.e. in accordance with the approved product label, and the instructions of the physician for the duration of the study – Screening to Follow-Up contact):

- Abstinence
- Oral contraceptive either combined or progestogen alone

- Injectable progestogen
 - Implants of levonorgestrel
 - Estrogenic vaginal ring
 - Percutaneous contraceptive patches
 - Intrauterine device (IUD) or intrauterine system (IUS)
 - Male partner sterilization (vasectomy with documentation of azoospermia) prior to the female subject's entry into the study and this male is the sole partner for that subject.
 - Double barrier method condom and an occlusive cap (diaphragm or cervical/vault caps) with a vaginal spermicidal agent (foam/gel/film/cream/suppository).
5. **COPD History:** An established clinical history of COPD in accordance with the definition by the American Thoracic Society/European Respiratory Society [Celli, 2004] as follows:
- Chronic obstructive pulmonary disease is a preventable and treatable disease state characterized by airflow limitation that is not fully reversible. The airflow limitation is usually progressive and is associated with an abnormal inflammatory response of the lungs to noxious particles or gases, primarily caused by cigarette smoking. Although COPD affects the lungs, it also produces significant systemic consequences.
6. **Tobacco Use and Smoking History:** Current or former cigarette smokers with a history of cigarette smoking of ≥ 10 pack-years [Number of pack years = (number of cigarettes per day /20) x number of years smoked (e.g. 20 cigarettes per day for 10 years, or 10 cigarettes per day for 20 years both equal 10 pack years)]. Former smokers are defined as those who have stopped smoking for at least 6 months prior to Visit 1.
- Note: Pipe and/or cigar use cannot be used to calculate pack-year history. COPD patients who only use a pipe and/or cigar are not eligible.
7. **Severity of Disease:** A pre and post-salbutamol/albuterol FEV₁/FVC ratio of <0.70 and a pre and post-salbutamol/albuterol FEV₁ of $\leq 70\%$ of predicted normal values calculated using National Health and Nutrition Examination Survey (NHANES) III reference equations at Visit 1 [Hankinson, 1999, Hankinson, 2010].
8. **Dyspnea:** A score of ≥ 2 on the Modified Medical Research Council Dyspnoea Scale (mMRC) at Screening (Visit 1)

4.3. Exclusion Criteria

Deviations from exclusion criteria are not allowed because they can potentially jeopardize the scientific integrity of the study, regulatory acceptability or subject safety. Therefore, adherence to the criteria as specified in the protocol is essential.

Subjects meeting any of the following criteria **must not** be enrolled in the study:

1. **Pregnancy:** Women who are pregnant or lactating or are planning on becoming pregnant during the study.
2. **Asthma:** A current diagnosis of asthma.
3. **Other Respiratory Disorders:** Known α -1 antitrypsin deficiency, active lung infections (such as tuberculosis) and lung cancer are absolute exclusionary conditions. A subject, who in the opinion of the investigator has any other significant respiratory conditions in addition to COPD should be excluded. Examples may include clinically significant bronchiectasis, pulmonary hypertension, sarcoidosis or interstitial lung disease.
4. **Other Diseases/Abnormalities:** Subjects with historical or current evidence of clinically significant cardiovascular, neurological, psychiatric, renal, hepatic, immunological, endocrine (including uncontrolled diabetes or thyroid disease) or haematological abnormalities that are uncontrolled and/or a previous history of cancer in remission for <5 years prior to Visit 1 (localized carcinoma of the skin that has been resected for cure is not exclusionary). Significant is defined as any disease that, in the opinion of the investigator, would put the safety of the subject at risk through participation, or which would affect the efficacy or safety analysis if the disease/condition exacerbated during the study.
5. **Chest X-Ray:** A chest X-ray or computed tomography (CT) scan that reveals evidence of clinically significant abnormalities not believed to be due to the presence of COPD. A chest X-ray must be taken at Visit 1 if a chest X-ray or CT scan is not available within 6 months prior to Visit 1.
6. **Contraindications:** A history of allergy or hypersensitivity to any anticholinergic/muscarinic receptor antagonist, beta₂-agonist, lactose/milk protein or magnesium stearate or a medical condition such as of narrow-angle glaucoma, prostatic hypertrophy or bladder neck obstruction that, in the opinion of the study physician contraindicates study participation or use of an inhaled anticholinergic.
7. **Hospitalization:** Hospitalization for COPD or pneumonia within 12 weeks prior to Visit 1.
8. **Lung Resection:** Subjects with lung volume reduction surgery within the 12 months prior to Screening (Visit 1).
9. **12-Lead ECG:** An abnormal and significant ECG finding from the 12-lead ECG conducted at Visit 1, including the presence of a paced rhythm on a 12-lead electrocardiogram (ECG) which causes the underlying rhythm and ECG to be obscured. Investigators will be provided with ECG reviews conducted by a centralized independent cardiologist to assist in evaluation of subject eligibility. Specific ECG findings that precluded subject eligibility are listed in [Appendix 3](#): The study investigator will determine the medical significance of any ECG abnormalities not listed in [Appendix 3](#).
10. **Screening Labs:** Significantly abnormal findings from clinical chemistry and haematology tests at Visit 1.
11. **Medications Prior to Spirometry:** Unable to withhold albuterol/salbutamol for the 4 hour period required prior to spirometry testing at each study visit.

12. Medications Prior to Screening: Use of the following medications according to the following defined time intervals prior to Visit 1; ([Table 1](#))

Table 1 Time Interval for Prohibited Medication Prior to Visit 1

Medication	Time Interval Prior to Visit 1
Depot corticosteroids	12 weeks
Systemic, oral, parenteral (intra-articular) corticosteroids	4 weeks
Antibiotics (for lower respiratory tract infection)	4 weeks
ICS/LABA combination products if ICS/LABA therapy is discontinued completely	30 days
Use of ICS at a dose >1000mcg/day of fluticasone propionate or equivalent ¹	30 days
Initiation or discontinuation of ICS use ¹	30 days
Phosphodiesterase 4 (PDE4) inhibitors (e.g. roflumilast)	14 days
Long-acting anticholinergics (e.g., tiotropium and aclidinium, glycopyrionium)	7 days
Theophyllines ²	12 hours (stable dose of theophylline alone is allowed during the study but must be withheld 12 hours prior to each study visit)
Oral leukotriene inhibitors (zaflurkast, montelukast, zileuton)	48 hours
Oral beta ₂ -agonists	
Long- acting	48 hours
Short –acting	12 hours
Olodaterol and Indacaterol (inhaled long-acting beta ₂ -agonist)	14 days
Salmeterol, formoterol, (inhaled long-acting beta ₂ -agonist)	48 hours
LABA/inhaled corticosteroid (ICS) combination products only if discontinuing LABA therapy and switching to ICS monotherapy ³	48 hours for LABA component
Inhaled sodium cromoglycate or nedocromil sodium	24 hours
Inhaled short acting beta2-agonists ⁴	4 hours
Inhaled short-acting anticholinergics ² (e.g. ipratropium bromide)	4 hours (stable dose of ipratropium alone is allowed during the study, provided that the subject is on a stable dose regimen from Screening (Visit 1 and remains so throughout the study) but must be withheld 4 hours prior to each study visit)
Inhaled short-acting anticholinergic/short-acting beta ₂ -agonist combination products	4 hours

Medication	Time Interval Prior to Visit 1
Any other investigational drug	30 days or 5 half lives, whichever is longer

1. Use of ICS is permitted provided the dose not exceed 1000mcg of fluticasone propionate or equivalent; ICS use not to be initiated or discontinued within 30 days prior to Visit 1
2. Ipratropium bromide or theophylline is permitted, provided that the subject is on a stable dose from Screening (Visit 1) and remains on the stable dose throughout the study; however, Ipratropium bromide must be withheld for 4 hours; theophylline must be withheld for 12 hours prior to and during each clinic visit.
3. The dose of ICS must be equivalent to that contained in the ICS/LABA combination product (the study procedures manual will have equivalence guidelines)
4. Use of study provided albuterol/salbutamol is permitted during the study, except in the 4-hour period prior to spirometry testing

13. Oxygen: Use of long-term oxygen therapy (LTOT) described as oxygen therapy prescribed for greater than 12 hours a day. As-needed oxygen use (i.e., \leq 12 hours per day) is not exclusionary.

14. Nebulized Therapy: Regular use (prescribed for use every day, not for as-needed use) of short-acting bronchodilators (e.g., albuterol/salbutamol) via nebulized therapy.

15. Pulmonary Rehabilitation Program: Participation in the acute phase of a pulmonary rehabilitation program within 4 weeks prior to Visit 1. Subjects who are in the maintenance phase of a pulmonary rehabilitation program are not excluded.

16. Drug or Alcohol Abuse: A known or suspected history of alcohol or drug abuse within 2 years prior to Visit 1.

17. Affiliation with Investigator Site: Is an investigator, sub-investigator, study coordinator, employee of a participating investigator or study site, or immediate family member of the aforementioned that is involved in this study.

18. Compliance: A subject will not be eligible if he/she has any infirmity, disability, illiteracy, disease, or geographical location which seems likely (in the opinion of the Investigator) to impair compliance with any aspect of this study protocol, including visit schedule and completion of daily diaries or questionnaires.

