Cardiovascular effects such as cardiac arrhythmia, e.g. atrial fibrillation and tachycardia.	
A potential class effect associated with anti-muscarinic therapies.
 
The clinical significance of these arrhythmias is unknown. Clinical experience with UMEC to date in completed studies has not shown any association with major cardiovascular events. Data available to date in the IB for UMEC [GlaxoSmithKline Document Number RM2006/00835/11 effective date 10-AUG-2015)
	
Exclusion criteria have been set for subjects with uncontrolled or severe cardiovascular disease according to the PI's opinion where the potential risk may outweigh the benefit.
 
An abnormal and significant ECG finding from the 12-lead ECG conducted at Visit 1, including the presence of a paced rhythm on a 12-lead ECG which causes the underlying rhythm and ECG to be obscured will be excluded. Specific ECG findings that precluded subject eligibility are listed in Appendix 2: The study investigator will determine the medical significance of any ECG abnormalities not listed in Appendix 3.

Narrow-angle glaucoma, urinary	
No association has been found to date, in completed studies with UMEC on glaucoma or urinary retention. However, glaucoma or urinary retention have been observed with other antimuscarinic agents, and could potentially be due to the pharmacology. Data available in the IB for UMEC [GlaxoSmithKline Document Number RM2006/00835/11 effective date 10-AUG-2015)
	
Exclusion criterion states that subjects with medical conditions such as narrow-angle glaucoma, prostatic hypertrophy, or bladder neck obstruction should only be included if, in the opinion of the study physician, the benefit outweighs the risk.

Paradoxical bronchospasm	Known effect associated	If paradoxical

Potential Risk of Clinical Significance	Summary of Data/Rationale for Risk	Mitigation Strategy
that may occur with an immediate increase in wheezing after dosing.	with inhalation therapy.	bronchospasm occurs following dosing with IP, this treatment should be discontinued immediately and alternative therapy should be instituted

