11.2. Appendix 2: 12-Lead ECG Exclusion Criteria

An abnormal and clinically significant finding that would preclude a subject from entering the trial is defined as a 12-lead tracing that is interpreted as, but not limited to, any of the following:

- Sinus tachycardia ≥ 120 bpm

*Note: sinus tachycardia ≥ 120 bpm should be confirmed by two additional readings at least 5 minutes apart

- Sinus bradycardia < 45 bpm

*Note: Sinus bradycardia < 45 bpm should be confirmed by two additional readings at least 5 minutes apart.

- Multifocal atrial tachycardia

- Supraventricular tachycardia (> 100 bpm)

- Atrial fibrillation with rapid ventricular response (rate > 120 bpm)

- Atrial flutter with rapid ventricular response (rate > 120 bpm)

- Ventricular tachycardias (non sustained, sustained, polymorphic, or monomorphic)

- Ventricular flutter

- Ventricular fibrillation

- Torsades de Pointes

- Evidence of Mobitz type II second degree or third degree atrioventricular (AV) block

- AV dissociation

- Trifascicular Block

- For subjects **with QRS duration < 120 ms**: QTc(F) ≥ 450 msec or an ECG that is unsuitable for QT measurements (e.g., poor defined termination of the T wave).

- For subjects **with QRS duration > 120** : QTc(F) ≥ 480 msec or an ECG that is unsuitable for QT measurements (e.g., poor defined termination of the T wave).

- Myocardial infarction (acute or recent) * Note: Evidence of an old (resolved) myocardial infarction is not exclusionary.

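### Exclusion criterion 9 sends sites to the ECG withdrawal list (Appendix 3) instead of the ECG exclusion list (Appendix 2), and three limits are looser there

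*Protocol*

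**What the plan says.** **Criterion 9 (Protocol Section 4.3)** excludes subjects with an abnormal and significant ECG at Visit 1. It refers to an appendix twice:

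- for the findings that bar entry: "Specific ECG findings that precluded subject eligibility are listed in [Appendix 3";
- for what is left to the investigator: "The study investigator will determine the medical significance of any ECG abnormalities not listed in [Appendix 3".

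It also provides for central review: "Investigators will be provided with ECG reviews conducted by a centralized independent cardiologist to assist in evaluation of subject eligibility". The introduction to Section 4.3 allows no deviations from the criteria and adds: "Therefore, adherence to the criteria as specified in the protocol is essential".

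**The risk table (Protocol Section 1.3)** carries the same pair of statements, but with two different appendices. The first is "Specific ECG findings that precluded subject eligibility are listed in Appendix 2"; the second is "The study investigator will determine the medical significance of any ECG abnormalities not listed in Appendix 3".

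**The appendices.** Appendix 2 (Section 11.2) is titled as the ECG exclusion criteria and opens: "An abnormal and clinically significant finding that would preclude a subject from entering the trial is defined as a 12-lead tracing". Appendix 3 (Section 11.3) is titled as the ECG withdrawal criteria and states that it applies after randomisation.

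**Withdrawal criterion 4 (Protocol Section 4.5)** refers twice to Section 11.3, which is correct for withdrawal.

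**The concern.** Criterion 9 decides who may enter on ECG grounds, and as written it names the list meant for deciding who must leave. That would be harmless if the two lists had the same limits, but they do not. A withdrawal list tolerates slower heart rates and longer QTc(F) than an entry list.

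The second pointer makes the error concrete, because it sets the boundary between mandatory exclusion and investigator judgement. An ECG that Appendix 2 excludes outright can count as not listed in Appendix 3, and so become a matter of opinion. Two sites could then decide differently on the same tracing, one following criterion 9 and the other following Appendix 2. Section 1.3 gives ECG exclusion as a mitigation for the cardiovascular risk of antimuscarinic drugs, so what is at stake is subject safety and consistent eligibility, not the efficacy estimate.

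**Working it through.** No formula applies. The check is to count the pointers, compare the two lists item by item, and read criterion 9 against each list.

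**1. Pointers to the ECG lists**

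| Place | Purpose | Points to | Correct? |
|---|---|---|---|
| 4.3 criterion 9, first | Findings that bar entry | Appendix 3 | No |
| 4.3 criterion 9, second | Limit of investigator judgement at entry | Appendix 3 | No |
| 1.3 risk table, first | Findings that bar entry | Appendix 2 | Yes |
| 1.3 risk table, second | Limit of investigator judgement at entry | Appendix 3 | No |
| 4.5 criterion 4, both | Withdrawal | Section 11.3 (Appendix 3) | Yes |

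There are 4 entry pointers, of which 3 are wrong, including both in the operative criterion.

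**2. Item comparison**

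Appendix 2 has 16 items and Appendix 3 has 19.

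- 13 are identical in both.
- 3 appear in both with looser limits in Appendix 3.
- 3 appear only in Appendix 3: a heart-rate rise of at least 40 bpm, a QTcF rise of more than 60 msec, and an uncorrected QT above 600 msec.

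Check: 13 + 3 = 16, and 13 + 3 + 3 = 19.

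**3. The three limits that differ**

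The bradycardia entry limit, for example, is "Sinus bradycardia < 45 bpm"; in Appendix 3 it is below 37 bpm.

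| Finding | Appendix 2 (entry) | Appendix 3 (withdrawal) | Band between | Width |
|---|---|---|---|---|
| Sinus bradycardia | < 45 bpm | < 37 bpm | 37–44 bpm | 45 − 37 = 8 bpm |
| QTc(F), QRS < 120 ms | ≥ 450 msec | ≥ 500 msec | 450–499 msec | 500 − 450 = 50 msec |
| QTc(F), QRS > 120 ms | ≥ 480 msec | ≥ 530 msec | 480–529 msec | 530 − 480 = 50 msec |

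The bands are written for readings in whole bpm and whole msec.

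**4. Criterion 9 read with each list**

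- *With Appendix 2:* all three bands are mandatory exclusions.
- *With Appendix 3:* all three bands are unlisted and pass to the investigator, with central review to help. Values beyond the withdrawal limits, and ECGs unsuitable for QT measurement, are excluded on either reading. This reading also adds an uncorrected QT above 600 msec as an exclusion. The two change-from-baseline items have no meaning at screening.

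The literal reading also removes the margin between entry and withdrawal. A subject with QRS below 120 ms admitted at 499 msec would meet the withdrawal limit of 500 msec after a rise of 500 − 499 = 1 msec. Section 4.5 does not allow withdrawn subjects to be replaced.

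**5. Likely origin**

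The amendment log shows that Appendix 3 was once the exclusion list and that a pharmacogenetic Appendix 1 was later removed. The pointers look like leftovers from that renumbering. This only explains the cause; the contradiction lies entirely within the current text.

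**The case against.** The strongest reply is that no careful reader would be misled. Following criterion 9 leads to a list headed as withdrawal criteria, with items that cannot apply at screening, directly after a list headed as exclusion criteria. Appendix 2 defines what bars entry in its own words, close to the opening of criterion 9, so it arguably operates without any pointer. The instruction to follow the criteria as the protocol specifies them covers Appendix 2 too. The first pointer in Section 1.3 is right.

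There are also safeguards. A central cardiologist reviews the Visit 1 ECG. Section 4.4 rests ECG eligibility on that overread and also requires no significantly abnormal pre-dose ECG at Visit 2. Both lists are open-ended, so an investigator could exclude a subject in these bands anyway. On this view the matter is editorial.

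Much of this stands. The intended list can be identified, so the protocol contradicts itself rather than plainly dropping a limit. But inferring the right list requires the site to override the text of the criterion it was told to follow. Central review assists and does not decide. The Visit 2 check states no numerical limits, and the central overread of that day's ECG is not available for it. These points reduce the likely harm; they do not make criterion 9 correct.

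**Conclusion.** The concern holds. Criterion 9 is wrong in both of its appendix references, and the second ECG reference in Section 1.3 is wrong in the same way: 3 of 4 entry pointers. On a literal reading, 3 of the 16 Appendix 2 limits relax to the withdrawal limits and the bands between pass to investigator judgement. The other 13 items are the same either way. The limits in the two appendices are not themselves in dispute.

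The practical size is unknown. The documents give no ECG distribution, so the number of subjects in the bands cannot be estimated and may be zero, and nothing indicates that a site applied the wrong list. The primary analysis is untouched: SAP Table 10 (Section 10.1.2.1) does not count failure of the 12-lead ECG exclusion as a deviation affecting the primary outcome. Sample size, power and alpha do not depend on it. This is a should-fix correction to a safety criterion, not a threat to the trial's conclusion.

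**What to change.** - In Section 4.3, criterion 9, change both references from Appendix 3 to Appendix 2.
- In the Section 1.3 risk table, change the second ECG reference from Appendix 3 to Appendix 2.
- Leave Section 4.5 pointing to Section 11.3 (Appendix 3).
- Send sites a short clarification that Appendix 2 governs entry.
- Optionally, check the Visit 1 overread ECGs already on file for values in the three bands.

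With these changes all three bands become mandatory exclusions again under criterion 9. The cost is three pointer corrections and one site notice, with no change to sample size, procedures or analysis.
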